## 6.0 Measurement of Effect

### 6.1 Antitumor Effect- Solid Tumors

Response and progression will be evaluated in this study using the new international criteria proposed by the Response Evaluation Criteria in Solid Tumors (RECIST) Committee [JNCI 92(3):205-216, 2000]. Changes in only the largest diameter (unidimensional measurement) of the tumor lesions are used in the RECIST v1.1 criteria.

### 6.1.1 Definitions

Evaluable for toxicity. All subjects will be evaluable for toxicity from the time of their first treatment with SABR.

Evaluable for objective response. Only those subjects who have measurable or non-measurable disease present at baseline, have received ALL fractions of SABR and have had their disease re-evaluated with a minimum of one year of follow up will be considered evaluable for response. These subjects will have their response classified according to the definitions stated below.

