Based on the published retrospective and the two prospective phase I trials, the dose fractionations evaluated in this trial is 8Gy x 5, 10Gy x 4 and 12 Gy x 3. In a retrospective study published paper by Wersäll, et al, from the Karolinska Hospital, 50 patients with kidney cancer, both primary and metastatic, were retrospectively analyzed [50]. High rates of local control were achieved with doses ranging from 25 Gy to 45 Gy. The most common doses used were 40 Gy in 5 fractions and 45 Gy in 3 fractions. Another retrospective study used the dose of 40Gy in 5 fractions and both studies reported excellent control rate [45]. Therefore 8Gy x 5 is evaluated in this study. The 4 and 3 fraction equivalent doses to this dose levels are 10Gy and 12 Gy respectively, which are the two other dose levels included in this trial. Justification of the three fraction dose equivalent of 12Gy x 3 comes from the phase I study that did not see any failures at this level.

The study population for this trial is patients with biopsy proven primary RCC that are candidates for active surveillance (AS). Keeping patient safety in perspective, it is reasonable to offer an experimental treatment such as this to a patient population that would have otherwise been put in AS. At any sign of progression, the patients that have undergone SABR in this trial will be offered the standard of care (SOC) of radical nephrectomy, partial nephrectomy or ablation as deemed appropriate by the treating urologist—which is same as what would have been offered to them had they been in AS. The AUA defines AS patients to be those with small renal mass (SRM) with <3cm tumors. The NCCN recommends AS for patients with T1a tumors or tumors <4 cm. A number of retrospective and one prospective study reported on the natural history of SRMs [51-55]. A meta-analysis reviewed multiple retrospective studies and reported an average growth rate of 0.28 cm/year for these tumors [51]. They further reported a growth of 0.4 cm/year in the subset of patients that had biopsy confirmed RCC. Keeping clinical application in perspective, it is logical to use SABR only to tumors that are growing, since one third of the SRMs do not grow. Therefore, patients

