**4.13 Subject Replacement**

The following are criteria for subject replacement: 1) If the subjects decide to withdraw from the study without finishing the course of SABR, 2) if the subjects decide to withdraw from the study or lost to follow up (for reasons of death from other causes, moving to other state etc.) or refuse follow up scans leading to <3 follow-up scans or <1 year of follow up, 3) if the subjects become unable to undergo an MRI or contrast enhanced CT scan with <1 year of follow up.

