**5.3 Follow-up Procedures**

Subject will be followed at every six months (+/- 2 weeks) thereafter for five years after their first follow up at 1 month (+/- 1 week).

With every visit, patients will have:

- Physical exam including: vital signs, weight, height and BMI
- MRI with or without contrast or CT with contrast
- Renal scintigraphy scan at 1 year
- Hematology
- Serum Chemistries
- Urine Analysis
- Lab corollary blood draw at 1 month and six month
- Performance status
- Toxicity evaluation
- Tumor measurements

**\*Note:** Subjects who show progressive disease or develop a new primary will be followed for survival only and will no longer strictly adhere to study calendar.

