## 5.5 Removal of Subjects from Study

Subjects can be taken off the study treatment and/or study at any time at their own request, or they may be withdrawn at the discretion of the investigator for safety, behavioral or administrative reasons. The reason(s) for discontinuation will be documented and may include:

- 5.5.1 Subject voluntarily withdraws from treatment (follow-up permitted);
- 5.5.2 Subject withdraws consent (termination of treatment and follow-up);
- 5.5.3 Subject is unable to comply with protocol requirements;
- 5.5.4 Subject demonstrates disease progression (follow-up permitted)
  - 5.5.4.1 Tumor size >4cm
  - 5.5.4.2 Loco-regional progression as defined in AJCC 7; stage >T1a.
- 5.5.5 Subject experiences toxicity that makes continuation with the remaining SABR fractions unsafe;
- 5.5.6 Treating physician judges continuation on the study would not be in the subject's best interest;
- 5.5.7 Subject becomes pregnant (pregnancy to be reported along same timelines as a serious adverse event) prior to the completion of SABR treatments;
- 5.5.8 Subject becomes unable to undergo imaging studies after enrollment, subject will be either replaced or withdrawn from study based on investigator's assessment;
- 5.5.8 Development of second malignancy (except for basal cell carcinoma or squamous cell carcinoma of the skin) that requires systemic treatment which could interfere with this study;
- 5.5.9 Lost to follow-up. If a research subject cannot be located to document survival after a period of 2 years, the subject may be considered "lost to follow-up." All attempts to contact the subject during the two years must be documented and approved by the Data Monitoring Committee.

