#### **6.1.4 Response Criteria**

##### **6.1.4.1 Evaluation of Lesions**

Complete Response (CR): Disappearance of all target lesions. Disappearance of all target lesions. Any pathological lymph nodes (whether target or non-target) must have reduction in short axis to <10 mm (the sum may not be "0" if there are target nodes). Determined by two separate observations conducted not less than 4 weeks apart. There can be no appearance of new lesions.

Partial Response (PR): At least a 30% decrease in the sum of the longest diameter (LD) of target lesions, taking as reference the baseline sum LD. There can be no appearance of new lesions.

Progressive Disease (PD): > 20% increase in the SLD taking as reference the smallest SLD recorded since the treatment started (nadir) and minimum 5 mm increase over the nadir.

Stable Disease (SD): Neither sufficient shrinkage to qualify for PR nor sufficient increase to qualify for PD, taking as reference the smallest sum LD since the treatment started. There can be no unequivocal new lesions.

Tumor Growth (TG): At least a 4mm increase in the LD of treated lesion in a single scan when compared to baseline scan (or an increase of >2.0mm in two consecutive scans).

Local Control: No TG AND a complete radiographic or pathologic absence of tumor viability.

Local Failure: Any TG OR any radiographic or pathologic evidence of tumor viability.

Indeterminate Disease Response: (IDR): 1) Presence of radiographic evidence of viable disease without any increase in the LD (<4mm) sufficient enough to qualify for TG; 2) complete absence of radiographic evidence of viable disease regardless of any change in tumor diameter.

A biopsy is recommended in the case of tumors with ≥4mm increase in size with no radiographic evidence of viable tumor, OR any tumors with radiographic evidence of viable tissue.

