## 9.0 STATISTICAL CONSIDERATIONS

### 9.1 Study Design/Study Endpoints

This is an open label single-arm phase II non-randomized prospective single arm study that treats a single SRM with SABR. The primary objective is local control of the SRMs. Local control is defined as less than 4mm increase in the longest diameter of tumor measured using either MRI or contrast enhanced CT scan and with no radiographic or pathologic evidence of viable tumor. The endpoint will be measured at a minimum follow up of one year. Secondary objections and endpoints explore the safety, toxicity, growth, growth rate, local failure, IDR, immune response and progression of the SRMs after SABR.

The stopping rules for this study include any treatment-related >grade 3 toxicity. If there are any treatment related grade 3 acute toxicity in >30% of enrolled patients after enrollment of at least 6 patients, the study will be suspended until permitted by a safety review.

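### Read literally, the one-year evaluability rule can leave a tumour that fails and is removed in the first year out of the local control rate

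*Protocol*

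**What the plan says.** Protocol 6.1.1 makes a patient evaluable for response only if they "have received ALL fractions of SABR and have had their disease re-evaluated with a minimum of one year of follow up". It continues: "These subjects will have their response classified according to the definitions stated below". The definitions that follow, in 6.1.4.1, include Local Control and Local Failure, the two sides of the primary endpoint. Section 9.1 sets the timing: "The endpoint will be measured at a minimum follow up of one year".

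Other sections govern what happens to a patient whose tumour fails early:

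- **1.3:** "At any sign of progression, the patients that have undergone SABR in this trial will be offered the standard of care (SOC"; the options listed are radical nephrectomy, partial nephrectomy or ablation, and no minimum time is set.
- **5.3:** scans are six-monthly, and patients with progressive disease "will be followed for survival only and will no longer strictly adhere to study calendar".
- **5.5.4:** a listed reason for removal is "Subject demonstrates disease progression (follow-up permitted"; follow-up is thus allowed but not required.
- **6.1.4.1:** "Local Failure: Any TG OR any radiographic or pathologic evidence of tumor viability". No time limit is attached.
- **4.13:** replacement covers patients who withdraw, are lost, or "refuse follow up scans leading to <3 follow-up scans or <1 year of follow up". A patient who has already failed is not exempted.

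Section 9.3 plans an exact binomial interval for the local control rate and names no denominator of its own.

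**The concern.** A year of observation is needed to say that a tumour is controlled. It is not needed to say that a tumour has failed. Section 6.1.1 applies the same one-year condition to both classes.

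The scheduled month-6 scan falls before the one-year assessment. If the tumour has failed by then and is removed at, say, month 8, there is no treated tumour left to assess at one year. Failure has itself caused the missing assessment, so an evaluability rule that needs the assessment selects on the outcome. The patient would leave the denominator without being counted as a failure.

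This is an open-label, single-arm trial of 16 patients, so one patient moves the primary estimate by several percentage points. Whether an early failure counts should not be left open until outcomes are known.

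**Working it through.** **1. The plan's own precision figure (9.2).** Inputs: p = 0.90, n = 16.

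SE = √(p(1−p)/n) = √(0.90 × 0.10 / 16) = 0.075, or 7.5%. Half-width = 1.96 × 7.5% = 14.7%, stated as 15%. The figure reproduces. The sample size is not at fault here; the denominator is.

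**2. Path of an early failure through the text.**

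| Step | Section | Consequence |
|---|---|---|
| Tumour growth or viability seen at month 6 | 6.1.4.1 | Meets Local Failure; no time limit |
| Surgery or ablation offered and accepted | 1.3 | Treated mass gone before one year |
| If classed as progressive disease | 5.3, 5.5.4 | Survival follow-up; further follow-up optional |
| Is the patient evaluable? | 6.1.1, 9.1 | Literal reading: no |
| Which class? | 6.1.4.1 through 6.1.1 | Literal reading: none |

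The first row makes the patient a failure and the last leaves the patient unclassified. The two cannot both stand.

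**3. Effect on the estimate.** Let N be the patients treated, F the failures, and d the failures removed in year one and left out. All other patients are taken as evaluable. The documents give no value for F or d, so both are assumptions.

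- All failures counted: (N − F)/N
- One-year evaluable only: (N − F)/(N − d)

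With N = 16 and Clopper-Pearson 95% intervals:

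| F | d | Rate | 95% CI |
|---|---|---|---|
| 2 | 0 | 14/16 = 87.5% | 61.7–98.4 |
| 2 | 1 | 14/15 = 93.3% | 68.1–99.8 |
| 2 | 2 | 14/14 = 100% | 76.8–100 |
| 4 | 0 | 12/16 = 75.0% | 47.6–92.7 |
| 4 | 1 | 12/15 = 80.0% | 51.9–95.7 |
| 4 | 2 | 12/14 = 85.7% | 57.2–98.2 |
| 4 | 3 | 12/13 = 92.3% | 64.0–99.8 |
| 4 | 4 | 12/12 = 100% | 73.5–100 |

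In these examples each omitted failure adds about 5 to 8 points (75.0 to 80.0 is 5.0; 92.3 to 100 is 7.7). The numerator is fixed and the denominator shrinks, so the movement is upward only.

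**4. In general.** If p is the true control rate and e the share of failures removed before one year, the control rate among evaluable patients is p / (p + (1 − p)(1 − e)).

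| True rate | e = 25% | 50% | 75% | 100% |
|---|---|---|---|---|
| 90% | 92.3% | 94.7% | 97.3% | 100% |
| 75% | 80.0% | 85.7% | 92.3% | 100% |

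**The case against.** The best defence is that no passage says in words that early failures are excluded. Section 6.1.1 can be read as satisfied by a month-6 re-evaluation in a patient then followed beyond month 12, since it does not say that the tumour must still be in place and scanned at one year. Local Failure has no time limit, a surgical specimen could supply pathologic evidence of viability, and 2.4.2.6 makes local failure a secondary endpoint in its own right. Section 4.12 asks for follow-up per protocol after removal from therapy. An analyst could properly count these patients. That reading is available, but nothing requires it, so the conflict stands.

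The route is also narrow. Growth of 4 mm by month 6 is 0.8 cm/year, twice the 0.4 cm/year that 1.3 quotes for biopsy-confirmed tumours, and the two-consecutive-scan criterion would not normally be met before month 12. Surgery is offered, not imposed, and 4.11 foresees continued scanning after growth. Progressive disease in 6.1.4.1 needs more than a 20% increase and at least 5 mm, so not every local failure triggers survival-only follow-up. All of this limits the likely number of cases, not the direction of the error.

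Two stronger inferences are not supported:

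- **That 4.13 replaces salvaged failures.** A reader might conclude that they are swapped for new patients, giving 16 evaluable patients out of 17 or more treated. Replacement is triggered by withdrawal, loss, refused scans or inability to be imaged; progression and salvage are not criteria. The remaining gap is only that a patient who has failed and later withdraws, is lost or refuses scans is not exempted.
- **That patients who stop SABR for toxicity (5.5.5) are hidden failures.** They do fall outside 6.1.1, but stopping for toxicity says nothing about local control. That is a separate choice of analysis set.

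Finally, 9.2 gives 90% as an expectation and sets no success threshold for local control, so crossing 90% triggers no formal decision.

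**Conclusion.** The concern holds as a conflict between stated rules. Sections 6.1.1 and 9.1 tie classification to one year of follow-up, while 1.3 and 5.3 describe a course in which an early failure may have no tumour to assess by then, and 6.1.4.1 defines failure without a time limit. Taken literally, 6.1.1 lets early salvaged failures leave the primary estimate, and the error can only favour the treatment. This is more than a detail left to an SAP, because the protocol itself states the restricting rule.

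The size is unknown. It depends on how many failures are removed before one year, from none (no bias) to all (an apparent rate of 100%). The worked counts are assumptions, not forecasts, and their intervals overlap widely. They show only that one or two patients are enough to change how the result reads.

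**What to change.** - **6.1.1 and 9.1:** require one year of follow-up only to score Local Control. Count documented Local Failure, or surgery or ablation of the treated mass for suspected failure, as failure in the denominator whenever it occurs.
- **4.13:** state that a patient who has already met Local Failure is not replaced on later withdrawal, loss or refusal of scans.
- **Sensitivity analysis:** report the strict one-year evaluable set alongside the primary result. Handle patients who stop SABR early for toxicity separately, and do not label them as failures.

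The cost is wording in three sections and a reported rate that may be slightly less favourable. No extra patients or procedures are needed, and no change to clinical management is implied.

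### The one-year evaluability rule has no clause keeping earlier documented local failures in the denominator, so any that leave follow-up bias the local control rate upward

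*Protocol*

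**What the plan says.** Protocol 6.1.1 requires all fractions of SABR for response evaluability, and adds that only subjects who "have had their disease re-evaluated with a minimum of one year of follow up will be considered evaluable for response". It continues: "These subjects will have their response classified according to the definitions stated below". The definitions that follow, in 6.1.4.1, include Local Control and "Local Failure: Any TG OR any radiographic or pathologic evidence of tumor viability"; the failure definition has no minimum time. Section 9.1 places the primary endpoint at a minimum follow-up of one year. Section 9.3 estimates the local control rate by the exact binomial method.

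Three other passages bear on who reaches one year:

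- **Section 1.3:** "At any sign of progression, the patients that have undergone SABR in this trial will be offered the standard of care", meaning nephrectomy or ablation.
- **Section 5.3:** "Subjects who show progressive disease or develop a new primary will be followed for survival only". Section 5.5 lists progression as a reason for removal, with follow-up permitted.
- **Section 4.13:** replacement is allowed for subjects who withdraw, are lost, or "refuse follow up scans leading to <3 follow-up scans or <1 year of follow up".

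**The concern.** Whether a subject counts in the primary analysis depends on reaching one year of re-evaluation, and an early local failure can be the reason for not reaching it. Once the mass has been removed or ablated, the treated tumour can no longer be re-evaluated at one year. No section says that a failure documented before one year stays in the denominator.

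Only failures can be lost by this route, so the error runs towards success. An exact confidence interval cannot correct it, and a single-arm trial has no comparator in which a similar loss might offset it. The replacement rule adds to the problem: it lets a new subject take the place of one whose failure is already on record. This is not a matter left open for a statistical analysis plan, because 6.1.1 itself states the evaluable set.

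**Working it through.** **The plan's own figure.** Section 9.2 gives n = 16, an expected local control rate of at least 90%, and a standard error of at most 7.5%. Check: √(0.9 × 0.1 / 16) = 0.075, and 1.96 × 0.075 = 0.147. The stated 7.5% and 15% (read as a half-width) are reproduced.

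**Can a failure precede one year?** Yes. The table in 5.4 puts MRI or CT at baseline and every six months, so scans fall at months 6 and 12. Growth or radiographic viability can be recorded at month 6.

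**Expected reported rate.** Let p be the true control rate and f the share of failures dropped. Controlled subjects stay (p) and a fraction f of the failures (1 − p) leaves, so

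reported rate = p / (1 − f(1 − p)).

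The documents give no value for f. It is an assumption, shown over a range:

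| True p | f = 0 | f = 0.25 | f = 0.5 | f = 0.75 |
|---|---|---|---|---|
| 90% | 90% | 0.9/0.975 = 92.3% | 0.9/0.95 = 94.7% | 0.9/0.925 = 97.3% |
| 80% | 80% | 0.8/0.95 = 84.2% | 0.8/0.90 = 88.9% | 0.8/0.85 = 94.1% |

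**In counts, without replacement.** Take 16 treated subjects with 3 failures: 13/16 = 81.3%. If two of the failures are early and dropped, the result is 13/14 = 92.9% (exact 95% CI 66.1% to 99.8%).

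**In counts, with replacement up to 16 evaluable.** Assume one later failure that is counted. The reported result is 15/16 = 93.8% (69.8% to 99.8%) however many early failures were dropped and replaced. Counting them gives:

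| Early failures dropped | Rate in all treated |
|---|---|
| 1 | 15/17 = 88.2% |
| 2 | 15/18 = 83.3% |
| 3 | 15/19 = 78.9% |
| 4 | 15/20 = 75.0% (50.9% to 91.3%) |

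In this example each dropped and replaced failure is worth about 4 to 6 points.

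**The scan-count trigger in 4.13.** On the 5.4 schedule the third follow-up scan falls at month 18. A subject who fails at the 12-month scan or biopsy and then withdraws has two scans, and so meets the replacement criterion in 4.13 while being evaluable under 6.1.1. The two rules do not agree.

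**The case against.** Much can be said for the plan, and some of it limits the point.

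- **Leaving is not automatic.** A reader might infer that every subject with growth at six months leaves imaging. The documents do not support that. The survival-only note in 5.3 applies to progressive disease or a new primary. Progressive disease in 6.1.4.1 needs an increase of more than 20% and at least 5 mm over nadir, whereas Tumor Growth needs 4 mm in a single scan. Section 4.11 continues imaging after growth at a frequency set by the physician. Section 4.12 asks for follow-up per protocol after removal from therapy. Surgery or ablation is offered, not required.
- **Replacement is narrower than it may look.** Progression and surgery are not replacement criteria. A reader might infer that a subject with a complete one-year assessment can be replaced on scan count alone, but that limb applies only after withdrawal, loss or refused scans. Section 4.13 also does not say that a replaced subject leaves the analysis. The count of two scans rests on the 5.4 table; the visit list in 5.3 could be read as adding a scan at month 1.
- **Other exclusions have no shown direction.** A reader might add subjects with incomplete SABR, or those unable to be imaged, of whom 5.5 says the "subject will be either replaced or withdrawn from study based on" the investigator's assessment. Neither group is defined by local failure, and nothing in the protocol shows that losing them raises the rate.
- **Early failures appear elsewhere.** Time to progression and progression-free survival are estimated by Kaplan-Meier, local failure is a secondary endpoint, and the growth stopping rule in 7.4 uses enrolled patients.
- **The effect may be small.** At the expected 90%, losing half the failures means 16 × 0.10 × 0.5 = 0.8 of a patient and a shift of 4.7 points, less than the 7.5% standard error.

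These arguments reduce how often the loss would occur. They do not supply the missing rule. A careful team could count early failures, since the failure definition has no time limit, but no text requires it and 6.1.1 read literally excludes them.

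**Conclusion.** The point stands in a limited form. As written, 6.1.1 allows a documented local failure before one year to fall out of the primary denominator, and 4.13 allows a subject with a documented failure to be replaced after withdrawal, loss or refused scans. Any failure lost in this way moves the rate upward.

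The size is uncertain because the share lost is an assumption. At the protocol's expected 90% it is 2.3 to 7.3 points for f between 0.25 and 0.75; at a true 80% it is 4.2 to 14.1 points. If no failure precedes one year, or if all such subjects remain in imaging, it is zero. The documents do not show that the loss is certain, that growth alone ends follow-up, or that the other exclusions favour success. The sample size and stated precision are not affected.

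**What to change.** Amend 6.1.1 and 4.13 as follows:

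1. Any treated subject who meets the Local Failure definition on any scan or biopsy up to the 12-month assessment counts as a failure in the primary analysis, whatever the later follow-up.
2. No subject with a documented failure is replaced or removed from the denominator.
3. The scan-count trigger in 4.13 is aligned with the one-year evaluability rule, so that the two sections no longer disagree about a subject assessed at month 12.
4. The local control rate is reported in all treated subjects beside the evaluable set.

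The cost is a text amendment. No visits, scans or biopsies are added, and clinical management is unchanged. The drawback is that the reported rate may be lower.
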